6. DATA SAFETY MONITORING PLAN (DSMC)

A project Data and Safety Monitoring Board (DSMB) will be set up by the Protocol Director, and will monitor the experiments detailed in this IRB proposal. The initial task of the DSMB will be to review the protocol, procedures manual and consent form to identify any necessary modifications. If modifications are necessary, revisions will be reviewed by the DSMB prior to its recommendation on initiation of the project. Throughout the study any changes to the protocol will be submitted to the DSMB. The DSMB, based on its review of the protocol, will identify the data parameters and format of the information to be regularly reported. The DSMB will be

informed of the occurrence of any serious adverse events and immediately notified of fatal or lifethreatening events. The DSMB may at any time request additional information from the Project Director. Based on the review of safety data, the DSMB will make recommendations regarding the conduct of the study. These may include amending safety monitoring procedures, modifying the protocol or consent, terminating the study, or continuing the study as designed. The discussions and

decisions of the DSMB will be summarized in written reports and provided to the Project Director. The DSMB will meet in person or by conference call on a quarterly basis. The DSMB will also provide advice regarding any discrepancies found by the data auditing system or other sources.

7. **BENEFITS**

MDD patients will receive at no cost of rTMS, a new FDA approved, noninvasive treatment for MDD. Note that all subjects in this study will receive rTMS. The long-term benefit for society may be a more detailed understanding of MDD and mechanisms of change in rTMS, as well as the basis for development of a novel TMS treatment for MDD. All participants will be given pictures of their brain collected during fMRI sessions.

8. **PRIVACY AND CONFIDENTIALITY**

All participant information and specimens are handled in compliance with the Health Insurance Portability and Accountability Act (HIPAA) and privacy policies of Stanford University, Stanford Health Care, and Stanford Children's Health.

During screening, participants will meet in a private interview room with a member of the study team to sign the consent form, discuss the protocol, and determine suitability for enrollment. All interviews will be done in a private setting. Followup interactions will take place by private phone calls and emails to previously identified email addresses private to that participant. MRI and fMRI/TMS will take place in the MRI suite in the Lucas center, to which access is restricted except to study personnel. Similarly, rTMS treatments will be done in the TMS room in the Department of Psychiatry and Behavioral Science, to which access is restricted except to study personnel.

All data will be de-identified after acquisition. PHI and images or electronic data with PHI will be stored on physically secure and password protected computer servers behind a firewall.

Data and image files will be given a coded study ID number, and PHI removed from the raw data. The PI has the code key. Digital MRI images will be de-identified by Lucas Center staff at the time images are saved. MRI scans, from which facial information may be reconstructed (and thus an identifier) will be de-identified using conventional face stripping algorithms for MRI data.

9. CONSENT PROCEDURES

The persons obtaining consent will be one of the investigators, the study coordinator, or a research assistant, who have completed all required Stanford training in Human Subjects, Good Clinical Practice, and HIPPA, and have been trained to give informed consents. The consenting interview is always done after the potential research subject has been presented with a description

of the study and indicated interest in participating, and before any information is collected, or any questionnaires answered. The consenting interview typically takes place in one of the private interview rooms in the Department of Psychiatry. Enough time will be allowed in the consent discussion for the potential participant to make an informed decision, and to ask any and all questions they may have and discuss the study with the researchers. We estimate this will take between 30 minutes and one hour. The potential participant may take the consent home to discuss with family or others, and return later to sign it if they so desire. Every attempt will be made to ensure the participant does not feel coerced. We believe that the payment offered for participation is not great enough to entice a person to participate if they do not otherwise want to do so. Coercion and undue influence will be minimized by declaring all conflicts of interest should they exist, openly answering and soliciting any questions the subject may have and pointing them to online resources about TMS or fMRI if they want to read additional information about the techniques.

10. STATISTICAL ANALYSIS PLAN

For the depression group, t-tests and ANOVAs will be performed to examine the effect of rTMS treatment, compared to sham, on network activity by comparing the follow-up TMS/fMRI scan to the initial scan between those two groups (N=20/group) – doing so will determine the network changes associated with real rTMS, since we have a convincing sham control arm. Additionally, we will use multiple regressions to examine the relationship between network-level activity change and clinical response to rTMS treatment in the real treatment group. Baseline TMS/fMRI moderators of treatment response will be examined using multiple regressions in the real treatment group.

Power calculation: Not Applicable.

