In summary, TMS (single-pulse TMS and rTMS) are generally safe and well-tolerated, however, seizures remain a rare but significant adverse event. In our study, all stimulation parameters are determined to comply with the safety guidelines for TMS (Wasserman, 1998; Rossi et al., 2009). In the event of adverse effects related to MRI/fMRI scanning and TMS, safety coordinators and medical staff at the Lucas Center and CNI will be on-site for consultation and assistance. The Stanford University Hospital Emergency Room is less than a 5-minute walk from the Lucas Center or 10 minutes from CNI. Finally, [name], the PI of this study, is a licensed physician and will oversee all research clinicians and monitor any adverse situations that might arise during the course of 20-40 sessions of rTMS at the psychiatry outpatient clinic, as well as the MRI/fMRI scans.

c. Use of Deception in the Study

Not applicable

d. Use of Audio and Video Recordings

Not applicable

e. Alternative Procedures or Courses of Treatment

The alternative to participation is not participation.

f. Will it be possible to continue the more (most) appropriate therapy for the participant(s) after the conclusion of the study?

This will not be possible. Daily rTMS treatment for MDD is intended to be a brief course of intervention. We do offer open-label rTMS to patients in sham group.

g. Study Endpoint(s)

The endpoint of the study is fMRI/TMS scans post rTMS treatment. Although this study involves rTMS and sham treatment, our goal is to explore the brain circuit involved in clinical improvement in response to focal, non-invasive brain stimulation with rTMS, not the efficacy of rTMS vs sham. In addition, we do offer open-label rTMS to the sham group.

Primary Outcome Measure:

Clinician administered HAM-D

The Hamilton Depression Rating Scale (HAM-D) is a 24-item clinician-administered assessment utilized as a way of determining a patient's level of depression before, during, and after treatment. It takes approximately 15-20 minutes to complete the interview and score the results.

Exploratory Outcome Measures:

fMRI/TMS assessed neural network connectivity [Time Frame: Up to 3 months.] From pre- to post-treatment, improvement will be based on enhanced functional connectivity.

Implicit emotion regulation [Time Frame: Up to 3 months]

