3. BACKGROUND

a. Past Experimental and/or Clinical Findings

Depression is a highly prevalent and serious mental illness, has a lifetime prevalence of 16% (Kessler RC et al., 2003), and accounts for more global disability than any other illness (WHO, 2008). Studies such as STAR*D have illustrated the poor success rates of even the best-calibrated treatments. In fact, only 43% of STAR*D patients were able to achieve sustained recovery during the study period (Nelson, 2006). At the heart of this problem is the lack of a causal, mechanistic, neurobiological understanding of the pathophysiology of depression. Having such an understanding would allow the development of novel, neural network-targeting treatments.

We conducted resting-state functional connectivity (FC) analyses in a sample of 39 medicationfree depressed subjects and 38 healthy controls, seeding the FC analyses with regularly-placed spheres throughout the entire PFC. We analyzed the groupwise difference at each of these seeds, measured as the number of suprathreshold voxels at p<0.05, the regions of greatest abnormality are in the ECN, and in particular its DLPFC node. As the patient sample analyzed here is reflective of the sample to be recruited for the proposed study, these data lend further support to targeting the pMFG with TMS/fMRI and conceptualization of network-level abnormalities in depression within the context of ECN-DMN interactions.

To test for causal and directional interactions between the ECN and DMN, we conducted concurrent TMS/fMRI in 11 healthy subjects, targeting the pMFG (ECN) and compared it to targeting a more anterior prefrontal region (aMFG), which is part of a cingulo-insular emotional salience network. Stimulation of the pMFG resulted, as predicted by correlational neuroimaging studies, in deactivation of regions within the DMN, most strikingly in the VMPFC. This effect was not seen after stimulation of the aMFG, where activation in the dorsal cingulate and insula was more evident, demonstrating site- and network-specific effects of stimulation. Interestingly, the individual functional connectivity-localized pMFG site was 5.1cm [SD 0.48] anterior to the primary motor cortex, thus consistent with localization using the "5cm rule," but now framed in the conceptual context of the ECN/DMN. These data demonstrate, for the first time, a causal, inhibitory relationship between the ECN and DMN, and makes possible a novel translation to depressed patients.

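### The only active-versus-sham analysis leaves its network measure, number of tests, alpha and multiplicity control undefined, so its false-positive rate cannot be established, yet section 10 claims a definite finding from it

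*Combined protocol and SAP*

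**What the plan says.** Section 10 (Statistical Analysis Plan) of the combined protocol and SAP is the whole analysis plan.

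- **Between-arm analysis.** "t-tests and ANOVAs will be performed to examine the effect of rTMS treatment, compared to sham, on network activity". The data to be compared are given: "comparing the follow-up TMS/fMRI scan to the initial scan between those two groups (N=20/group".
- **Inference claimed from it.** "doing so will determine the network changes associated with real rTMS, since we have a convincing sham control arm".
- **Other analyses.** "we will use multiple regressions to examine the relationship between network-level activity change and clinical response to rTMS treatment in the real treatment group". Baseline moderators are also examined by regression, again in the active arm only.
- **Sample size basis.** "Power calculation: Not Applicable".

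Section 2g (Study Endpoint(s)) says "The endpoint of the study is fMRI/TMS scans post rTMS treatment". It then names the HAM-D as the primary outcome and places TMS/fMRI connectivity among the exploratory outcomes. Section 10 contains no active-versus-sham test of the HAM-D.

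Section 3a (Past Experimental and/or Clinical Findings) reports a pilot in 11 healthy subjects, in which stimulating the pMFG resulted "in deactivation of regions within the DMN, most strikingly in the VMPFC". Section 10 does not take up that region.

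**The concern.** The comparison between randomised arms carries all of the trial's randomised inference. A reader of section 10 knows which scans and which groups are compared. The reader does not know what is measured on the scans: which region, which pair of networks, or which summary. Nor does the plan say how many tests there will be, at what level, or with what correction. The two methods are named in the plural without saying which applies to what.

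An open search of this kind can be legitimate if it is presented as one. Here it is joined to wording that promises to establish the network effects of active treatment. If several regions or measures are tested and the smallest p-values are reported, a chance result could be presented as the mechanism of rTMS, and nothing fixed in advance would let anyone tell the difference.

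**Working it through.** **1. What can be reproduced.** The plan gives 20 per group, and 2 × 20 = 40, which agrees with the planned enrolment in section 5a. There is no alpha, power, effect size or number of tests to reproduce.

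**2. Inputs assumed.** Two-sided 5% per test, no correction, and k tests. The documents fix none of these, so k is varied.

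**3. Independent tests.** The chance of at least one false positive is 1 − 0.95^k.

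- k = 10: 1 − 0.95^10 = 0.401
- k = 20: 1 − 0.95^20 = 0.642

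**4. Correlated tests.** Measures from the same participants will be correlated, which lowers these figures. Two-sample t-tests with 20 per arm (38 degrees of freedom) were simulated under no effect, with equal correlation between measures and 20,000 trials per setting. The simulation standard error is at most √(0.25/20,000) = 0.0035.

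| Tests (k) | Independent | Correlation 0.5 | Correlation 0.8 |
|---|---|---|---|
| 1 | 5.0% | – | – |
| 3 | 14.3% | 12.6% | 10.0% |
| 6 | 26.5% | 20.4% | 13.9% |
| 10 | 40.1% | 29.4% | 17.8% |
| 20 | 64.2% | 43.7% | 23.3% |

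What the plan permits therefore runs from 5% (one contrast) to 64% at 20 independent uncorrected tests, and higher for more.

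**5. What one named contrast buys.** Power is from the noncentral t distribution with 20 per arm and an assumed standardised effect of 0.8 (noncentrality 0.8 × √(20/2) = 2.53).

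| Tests sharing 5% (Bonferroni) | Level per test | Power |
|---|---|---|
| 1 | 0.05 | 69% |
| 3 | 0.0167 | 52% |
| 10 | 0.005 | 34% |
| 20 | 0.0025 | 26% |

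A single prespecified contrast holds the error rate at 5% and keeps about twice the power of a Bonferroni correction over 10 tests (69/34 = 2.0). At an effect of 0.5 its power is 34%.

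**The case against.** The strongest reply is that the imaging outcome is labelled exploratory and that section 2g describes the aim as exploring a circuit, not testing efficacy. Strict familywise control is less expected for exploratory outcomes. That stands as far as it goes, and it is why a wholly exploratory analysis is an acceptable remedy. It does not settle the point, because the same section calls the scans the study's endpoint and section 10 uses the language of a definite finding. The label and the claim cannot both hold.

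Three stronger readings are tempting but are not supported.

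- **That the tests are unlimited and uncorrected.** The plan is silent. It sets no count and promises no correction, but it does not say that correction will be omitted.
- **That a chance finding is more likely than not.** One might take four measures from section 2g (TMS-evoked connectivity, task reaction time, task activation, resting connectivity), multiply by the three kinds of analysis in section 10, and get 12 tests and 1 − 0.95^12 = 46%. Even that is below half. Two of the three analyses are confined to the active arm, so at most 4 of the 12 compare arms: 1 − 0.95^4 = 18.5% if independent. Section 10 assigns only the TMS/fMRI scans to the between-arm comparison, so even 4 is conjecture.
- **That the pilot already supplies the confirmatory hypothesis.** The VMPFC result was an acute response to stimulation in healthy subjects. It says nothing direct about change after a treatment course in depressed patients, so it makes that region a candidate and no more.

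**Conclusion.** The point holds in this form: the between-arm contrast is stated, but the measure, number of tests, alpha and error control are not, so the false-positive rate cannot be established and the wording of section 10 claims more than the plan can deliver. If the tests were uncorrected at two-sided 5%, the rate would be about 18–40% for 10 tests and 23–64% for 20, the lower end at a correlation of 0.8 and the upper end at independence. Those ranges rest on assumed test counts, an assumed level and assumed absence of correction; they illustrate the exposure and do not estimate what the investigators will do. The change should be made, because this comparison is the trial's only randomised inference. It does not bear on participant safety.

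**What to change.** In section 10, prespecify one lead network contrast: the active-minus-sham difference in pre-to-post change in a named measure, analysed by ANCOVA with the baseline scan value as covariate, at two-sided 5%. The pMFG-evoked VMPFC or wider DMN response is a candidate; the text should note that the supporting pilot was acute and in healthy subjects. Report all other regions and modalities, and the active-arm regressions, as exploratory, with false-discovery-rate control or, for voxelwise maps, cluster-level familywise correction. Confine the claim to determine network changes to the lead contrast, and say in section 2g how that contrast stands in relation to the HAM-D as named primary outcome.

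If the sponsor prefers a wholly exploratory imaging analysis, change the verb in section 10 from determine to explore, bring the endpoint statement in section 2g into line, and keep the baseline adjustment and the correction.

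Either route needs only SAP and protocol wording and standard software options, with no new scans or participants. The costs are fewer secondary regions declared significant and, for the lead contrast, modest power: about 69% at an assumed standardised effect of 0.8. Baseline adjustment may raise that, by an amount that depends on the correlation between the two scans, which the documents do not give. The plan should state this limit where it now gives no power calculation.

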2. STUDY PROCEDURES

a. Procedures

All eligible subjects will undergo structured diagnostic interviews, including a MDD-specific assessment at Stanford shortly after recruitment. Subjects will then have a pre-treatment baseline MRI session (structural, resting), a concurrent fMRI/TMS scan session and a concurrent EEG/TMS session within two weeks at one of the Stanford scan sites. Preparation for physiological measurements will take 30-40 minutes including calibration time. These initial assessments provide a baseline for comparing pre- to post-treatment brain changes in patients. In the case of the baseline assessments, TMS is a probe for testing brain circuitry and as such, actual TMS must be used. All participants, whether randomized to active or sham, complete the TMS baseline assessments in order to provide baseline brain activation profiles.

After determining study eligibility, participants will wear an EEG cap which is like a swimming cap with Ag/AgCl electrodes which will be filled with gels through syringe. The Ag/AgCl electrodes for EOG.

Subjects will then be randomized to receive 4 weeks daily rTMS vs. sham (placebo) treatment sessions (total 20). For participants who receive sham (placebo) treatment for the first 4 weeks, they are offered 4 weeks of open-label active treatment. For participants who receive active

treatment during the first 4 weeks of treatment, they are not offered another 4 weeks of treatment.

Finally, another fMRI/TMS scan and EEG/TMS session will be scheduled within one week post rTMS treatment. Depression and anxiety will be evaluated using MDD and anxiety specific assessment pre and post- rTMS/sham treatment and after the 10th and 20th (and 30th and 40th for open-label patients) treatment session during rTMS/sham.

Patients who drop out of treatment will be encouraged to return for clinical and imaging assessments. Participants who continue onto the open-label treatment will also come in for another fMRI/TMS scan and EEG/TMS session within 1 week after their second 4 weeks of treatment.

b. Procedure Risks

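### The rTMS-versus-sham comparison of TMS/fMRI network activity names no baseline covariate; ANCOVA on the same two scans would usually be more precise at 20 per arm

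*Combined protocol and SAP*

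**What the plan says.** Section 10 (Statistical Analysis Plan) states that "t-tests and ANOVAs will be performed to examine the effect of rTMS treatment, compared to sham, on network activity", and that this is done "by comparing the follow-up TMS/fMRI scan to the initial scan between those two groups (N=20/group". No covariate is named and no ANCOVA is mentioned. Baseline imaging appears as a regressor only within the active arm: "Baseline TMS/fMRI moderators of treatment response will be examined using multiple regressions in the real treatment group". The power calculation is marked not applicable, and no SD, effect size, significance level or scan-to-scan correlation is given.

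Section 2a (Procedures) shows that the covariate will exist in both arms: "All participants, whether randomized to active or sham, complete the TMS baseline assessments in order to provide baseline brain activation profiles". After treatment, "another fMRI/TMS scan and EEG/TMS session will be scheduled within one week post rTMS treatment". The same section foresees people leaving treatment: "Patients who drop out of treatment will be encouraged to return for clinical and imaging assessments".

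Section 2g (Study Endpoints) says "The endpoint of the study is fMRI/TMS scans post rTMS treatment". It also lists HAM-D as the primary outcome measure and fMRI/TMS connectivity among the exploratory ones.

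**The concern.** With one scan before and one after treatment, a t-test on change and the group-by-time term of a two-by-two repeated-measures ANOVA are the same test. Both subtract the whole initial value from the follow-up value, that is, they fix the baseline slope at 1. When the two scans correlate less than almost perfectly, this carries noise from the initial scan into the estimated difference. ANCOVA estimates the slope from the data and removes only the part of the follow-up value that the initial scan predicts.

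This is the only between-arm test in the plan, and it is the one meant to show which network changes belong to real rTMS. With 20 per arm there is little precision to spare. What is at stake is a wider interval for the rTMS-sham difference than the same 40 patients could give. Bias and type I error are not at issue.

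**Working it through.** **Inputs from the documents.** 20 per arm (section 10), which agrees with planned enrolment: 2 x 20 = 40 (section 5a). Initial scan in both arms and one post-treatment scan (section 2a). The plan gives no power or precision figure, so there is nothing to reproduce.

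**Assumptions.** Correlation r between the two scans from 0.3 to 0.9; equal SD s at both scans and a common slope; two-sided 5%; true differences of 0.8 and 0.5 SD; one scalar network measure.

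**Formulas, n per arm.**
- Change score: Var = 2(1 - r)s² x 2/n, with 2n - 2 = 38 df.
- ANCOVA: Var = (1 - r²)s² x (2/n) x [1 + 1/(2n - 4)], with 2n - 3 = 37 df. The bracket is the cost of estimating the slope: 1 + 1/36 = 37/36 at n = 20.
- Ratio, ANCOVA to change score: (1 + r)/2 x 37/36.

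**Example, r = 0.5, s = 1.**
- Change score: 2 x 0.5 x 0.1 = 0.100, SE 0.316, 95% half-width 2.024 x 0.316 = 0.64.
- ANCOVA: 0.75 x 0.1 x 37/36 = 0.0771, SE 0.278, half-width 2.026 x 0.278 = 0.56.
- Ratio: 0.75 x 37/36 = 0.771. The change score needs 1/0.771 - 1 = 30% more patients for the same variance.

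**Results at 20 per arm** (change score vs ANCOVA; half-widths in SD units; power from the noncentral t):

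| r | Variance ratio | Extra patients for change score | 95% half-width | Power, 0.8 SD | Power, 0.5 SD |
|---|---|---|---|---|---|
| 0.3 | 0.67 | 50% | 0.76 vs 0.62 | 55% vs 72% | 26% vs 36% |
| 0.5 | 0.77 | 30% | 0.64 vs 0.56 | 69% vs 80% | 34% vs 42% |
| 0.7 | 0.87 | 14% | 0.50 vs 0.46 | 89% vs 93% | 51% vs 57% |
| 0.9 | 0.98 | 2% | 0.29 vs 0.28 | about 100% for both | 93% vs 94% |

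**Break-even.** Setting the ratio to 1 gives r = 2 x 36/37 - 1 = 0.946. Above that ANCOVA loses slightly. As r approaches 1 the ratio approaches 37/36, so the largest loss is 1/36, about 2.8% of variance.

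**Unequal SDs.** With follow-up SD k times the initial SD, the ratio is k²(1 - r²)/(1 + k² - 2rk) x 37/36. At r = 0.3, 0.5, 0.7 and 0.9 it is 0.52, 0.59, 0.65 and 0.63 for k = 0.8, and 0.81, 0.92, 1.01 and 0.98 for k = 1.25. ANCOVA is better or essentially equal throughout.

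**Missing second scans.** If 20% lacked a second scan (an assumption), 16 per arm would remain and the bracket becomes 29/28. Power for 0.8 SD at r = 0.3, 0.5 and 0.7 is then 46% vs 61%, 59% vs 70% and 81% vs 85%.

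**Simulation.** Variance ratios over 40,000 trials per value of r were 0.665, 0.766, 0.870 and 0.975 at r = 0.3, 0.5, 0.7 and 0.9, in line with the formula. In a separate run of 20,000 replicates per setting, type I error was 4.9% to 5.1% for both tests, and both gave a mean estimate of 0.80 when the true difference was 0.8.

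**Other reading.** If a t-test of the follow-up scan alone were meant, the difference detectable with 80% power would be 0.91 SD whatever r is. ANCOVA gives 0.92 at r = 0, 0.90 at r = 0.2, 0.88 at r = 0.3 and 0.80 at r = 0.5.

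**The case against.** The strongest reply is that the plan contains no error here. The planned test is valid, it already uses the initial scan, and no power target is missed because none is set. That is right, and it limits the point to efficiency.

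The size of the gain is also unknown. Nothing in the documents places r in the low-to-moderate range. At r = 0.8 the ratio is 0.925 and power for 0.5 SD is 68% vs 72%, a small gain; at 0.9 it is negligible. This stands as a limit on the size. It does not change the direction of the advice, since the loss is capped at about 2.8% of variance while the saving is 33% at r = 0.3 and 23% at r = 0.5.

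The change-score model is inferred, because the plan says only t-tests and ANOVAs. This too stands, and is itself a reason to write the model out.

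The power percentages assume one measure tested at 5%. If several regions or connections are tested with adjusted levels, those percentages no longer apply; the variance ratio still holds for each measure at its own r.

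The outcome is listed as exploratory as well as being called the study endpoint, so its weight is debatable. Finally, missing second scans weaken both analyses, and ANCOVA needs both scans too. Dropout makes precision scarcer, but does not by itself favour ANCOVA.

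**Conclusion.** The concern holds as a point of precision. The between-arm comparison names no covariate, although the initial scan is planned for everyone in both arms. If the planned test is one on change, with equal SDs, a common slope and 20 per arm, ANCOVA has the smaller variance for any r from 0 to about 0.946. The gain is material at low to moderate r: the 95% interval is 18% narrower at r = 0.3 (0.62/0.76 = 0.82) and 12% narrower at r = 0.5 (0.56/0.64 = 0.88). It is slight by r = 0.8 and negligible at 0.9. Confidence in the size is only moderate, because r is not given. The change should be made because it costs almost nothing; the trial's validity does not depend on it.

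**What to change.** In section 10, replace the between-arm t-test/ANOVA with wording such as:

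> For each TMS/fMRI network measure named before analysis, the post-treatment value will be compared between arms by ANCOVA, with arm as factor and the pre-treatment value of the same measure as covariate. The adjusted difference and its 95% confidence interval will be reported.

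The plan refers only to network activity, so the measure (region or connection, and contrast) has to be named first. The planned t-test needs that step as well.

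The cost is one sentence in the plan, the naming of the measure, and one degree of freedom (37 instead of 38 with 40 patients). No additional scans are needed.

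### The regression of clinical response on network change uses the active arm only, so it cannot show whether the association is particular to rTMS

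*Combined protocol and SAP*

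**What the plan says.** Participants are randomised between active and sham treatment (Section 2a: "Subjects will then be randomized to receive 4 weeks daily rTMS vs. sham (placebo) treatment sessions (total 20"). Section 10 then plans three analyses.

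1. t-tests and ANOVAs of network change, active against sham: "comparing the follow-up TMS/fMRI scan to the initial scan between those two groups (N=20/group".
2. Multiple regressions to "examine the relationship between network-level activity change and clinical response to rTMS treatment in the real treatment group".
3. Baseline predictors, also in one arm: "Baseline TMS/fMRI moderators of treatment response will be examined using multiple regressions in the real treatment group".

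The second analysis is the subject here. It is the only one that puts change in the network and change in the patient into the same model. No section plans it in the sham arm, in a pooled model or with an arm interaction.

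The data for a two-arm model are planned. Section 2a schedules ratings in both arms ("Depression and anxiety will be evaluated using MDD and anxiety specific assessment pre and post- rTMS/sham treatment"). The first analysis in Section 10 cannot be done without follow-up scans in sham participants. On the aim, Section 2g says "our goal is to explore the brain circuit involved in clinical improvement in response to focal, non-invasive brain stimulation with rTMS", and sets this apart from testing efficacy. The same section makes the HAM-D the primary outcome and lists the imaging measures as exploratory.

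**The concern.** Within one arm everyone has the same assigned treatment, so the slope of clinical change on network change reflects differences between patients. Some of those differences would arise without active stimulation: natural course, regression to the mean, daily clinic contact. If network activity follows mood whatever moves the mood, the active arm will show a correlation. It will also show one if the link exists only under rTMS. The sham arm can help to separate these two cases, and this analysis leaves it out.

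What is at stake is how far a positive result can be taken. A reader who comes to it from Section 2g will naturally take it as evidence about the circuit through which rTMS works. The active-only model does not carry that information.

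**Working it through.** **Inputs from the documents.** 20 per group (Section 10) and 40 in total (Section 5a); 2 × 20 = 40, so these agree. Section 10 marks the power calculation as not applicable, so there is no figure to reproduce.

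**Assumptions, because the documents give none.** Two-sided 5%; correlation r between network change and clinical change of 0.3 to 0.7; clinical effect of rTMS d of 0 to 0.8 SD; clinical response measured as HAM-D change. Section 2a says only "Patients who drop out of treatment will be encouraged to return for clinical and imaging assessments" and gives no dropout rate, so I show 20 per arm and, for 20% loss, 16 per arm.

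**Step 1: does the planned test separate the two cases?** Simulated trials with 20 per arm:

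| r | Active-only test, link in both arms | Active-only test, link in active arm only | Interaction, link in both arms | Interaction, link in active arm only |
|---|---|---|---|---|
| 0.3 | 25% | 25% | 5% | 15% |
| 0.5 | 64% | 64% | 5% | 34–35% |
| 0.6 | 84% | 84% | 5% | 48–49% |

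A hand check by Fisher's z, power ≈ Φ(atanh(r) × √(n − 3) − 1.96), at r = 0.5 and n = 20 gives Φ(0.549 × 4.123 − 1.96) = Φ(0.305) = 62%, close to the simulated 64%. The first two columns agree because the active-only test never sees the sham arm. This holds for any r.

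**Step 2: do the between-arm tests fill the gap?** Only in part. With r = 0.5 and d = 0.5, the between-arm test of network change is significant in 12% of trials in both cases. If the network only follows mood and rTMS improves mood by d = 0.8, it is significant in 24% (r = 0.5) to 41% (r = 0.7).

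**Step 3: what does the interaction not tell us?** Take r = 0.5 in both arms and compare two causal orders.

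- Mediation: rTMS shifts the network by 0.8 SD and the network drives mood. The active-only test rejects in 64% and the interaction in about 5%.
- Reverse order: rTMS shifts mood by 0.8 SD and the network follows. The active-only test rejects in 64% and the interaction in about 5%.

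The slopes are equal in both, so the interaction cannot distinguish them. The between-arm network test does differ. Its approximate power is Φ(δ × √(20/2) − 1.96), where δ is the network shift in SD. Mediation has δ = 0.8, so Φ(2.530 − 1.96) = 72% (about 70% by simulation). Reverse order has δ = 0.5 × 0.8 = 0.4, so Φ(1.265 − 1.96) = 24% (22–24% by simulation).

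**Step 4: how precise is a comparison of the arms?** The standard error of a difference between two Fisher z values is √(2/17) = 0.343, so the 95% half-width is 1.96 × 0.343 = 0.67. For r = 0.5 against 0 the difference is 0.549, with interval −0.12 to 1.22, and power is Φ(0.549/0.343 − 1.96) = 36% (simulation 35%; 28% at 16 per arm). For 80% power, n per arm = 3 + 2 × ((1.96 + 0.842)/atanh(r))², which rounds up to 56, 36 and 24 for r = 0.5, 0.6 and 0.7 against 0.

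**The case against.** The best defence has four parts.

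- Section 10 promises only to examine a relationship. It makes no causal or rTMS-specific claim for this regression, and it introduces it as an addition. That is right, and it limits the point to what the result can support.
- The objectives in Section 1b name the effect of rTMS on networks and the relation of baseline deficits to outcome, not change against change. That is also right. The importance of this regression is inferred from Section 2g, which speaks of exploring. A reader might infer that it is the trial's declared main analysis, but the documents do not say so.
- Sham is already used. A reader might infer from the single-arm regression that the trial cannot identify network change produced by rTMS. Section 10 does not support that: the average change is compared with sham. The gap is confined to the link between network change and clinical change.
- Equal slopes are what ordinary mediation predicts. It is tempting to say that an association counts as mechanism only if the slopes differ, or that equal correlations mean nothing is specific to rTMS. Step 3 shows why neither follows: under a true mediating pathway with a common slope, such a rule would dismiss the mechanism in about 95% of trials. Nor are 25%, 64% and 84% false-positive rates; in each case the correlation in the active arm is real.

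After all four, the active-only slope still has no comparator, although the plan collects one.

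**Conclusion.** The point holds in this limited form. The planned regression cannot show whether the association between network change and clinical response is particular to rTMS. That conclusion follows from the design and needs no assumed value. The rejection rates of about 25%, 64% and 84% rest on the assumed r of 0.3, 0.5 and 0.6, 20 complete participants per arm and two-sided 5%; at 16 per arm and r = 0.5 the rate is about 53%.

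A two-arm model would show whether the association differs between arms. It would not establish causal order, since both changes are measured over the same period, and at 20 per arm it would show only a large difference reliably. This is a worthwhile correction to an exploratory analysis. It does not undermine the randomised comparison of network change.

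**What to change.** In Section 10, replace the active-only regression with one model in all randomised participants: HAM-D change from baseline to session 20 on network change, arm, and arm × network change. State these points with it:

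- Each sham participant contributes the scan taken after sham and before any open-label treatment. Section 2a adds a later scan for those who go on to open-label rTMS, and Section 10 does not say whether they then count in the real treatment group.
- Report the slope in each arm and their difference with a 95% confidence interval.
- Read the slopes together with the between-arm difference in network change. Similar slopes mean that the association is not shown to be specific to rTMS; they do not rule out mediation. Neither result establishes causal order.
- Label the analysis exploratory.

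The cost is a change of SAP wording and one extra model on data already planned. The downside is the imprecise interaction (about 35% power for r = 0.5 against 0 at 20 per arm), so the conclusion will be more cautious.
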